7. TREATMENT COMPLIANCE

The investigator or designated study-site personnel will maintain a log of all study drug dispensed and returned. Drug supplies for each subject will be inventoried and accounted for throughout the study.

Study drug will be self-administered by subjects. As such the number of study drug dispensed will be recorded and compared with the number returned.

At study visits, study drug will be self-administered on site, which will be witnessed by designated study-site personnel at the study sites.

Subjects will receive instructions on compliance with study drug administration upon study medication (blisters) dispensed. During the course of the study, the investigator or designated study-site personnel will be responsible for providing additional instruction to re-educate any subject who is not compliant with taking the study drug.

Subjects who are no longer capable of ensuring treatment compliance in the judgment of the investigator (e.g. due to progression to dementia) have to be supported in study drug handling and administration (e.g. care giver or nurse practitioner). In case support cannot be provided subjects should be discontinued from treatment and withdrawn from the study.

8. PRESTUDY AND CONCOMITANT THERAPY

Prestudy therapies administered up to 30 days before screening must be recorded at screening.

Concomitant therapies must be recorded throughout the study beginning with signing of the initial informed consent until the End-of-Treatment visit (Follow-up visit). Concomitant therapies should also be recorded beyond this time only in conjunction with new or worsening adverse events until resolution of the event.

Progression of symptoms associated with AD should be recorded in the eCRF and any symptomatic treatment therefore will be documented until the End-of-Treatment visit (Follow up visit).

All therapies (prescription or over-the-counter medications, including vaccines, vitamins, herbal supplements; nonpharmacologic therapies such as electrical stimulation, acupuncture, special diets, exercise regimens) different from the study drug must be recorded in the CRF. Modification of an effective pre-existing therapy should not be made for the explicit purpose of entering a subject into the study.

Treatment with cognitive enhancers (e.g., cholinesterase inhibitors) or drugs intended for the treatment of cognitive deficits prior to enrollment in the extension study is allowed.

New therapies or therapy adaptations that are expected to have an impact on cognitive performance (e.g., cholinesterase inhibitors or memantine), will be permitted if clinically indicated, after notification of the Sponsor. Before a subject starts, stops or changes a dose of a therapy expected to have an impact on cognition, the Sponsor's medical monitor must be contacted in part to determine if specific clinical measures (e.g., cognitive measures) should be performed prior to the modification of concomitant medication regimen.

Use of benzodiazepines for treatment on an as-needed basis for insomnia or daily dosing as anxiolytics is permitted. If they are being given chronically, use of sedatives or hypnotics should be avoided for 24 hours before administration of cognitive tests. If sedating medication is given for MRI at any visit or for any short-term use, then all cognitive assessments must be administered at least 4 half-lives hours after administration of the sedative.

Stable use of pain medications will be permitted. Short-term use of narcotics is allowable if not administered within 4 half-lives hours prior to cognitive assessments.

Other concomitant medications that affect central nervous system (CNS) function may be given if efforts are made to keep the dose unchanged throughout the study. Doses of these compounds

should remain constant from 6 weeks prior to first dosing (Day 1 of the DB treatment phase). To avoid effects on cognitive measures, the following apply:

- Subjects should not stop receiving any medications that affect CNS function during the study
- Subjects should not add any medications that affect CNS function to the treatment regimen, unless medically necessary.
- Subject should not change doses of medication that affect CNS function

In cases of unforeseen starting, stopping or changing of stable doses of a therapy that affect CNS function occurs during the study, the Sponsor's medical monitor must be contacted to determine if the subject should continue in the study or not, and whether or not specific clinical measures (e.g., cognitive measures) should be performed.

In relation to CSF sampling, unless otherwise specified in this section, local site instructions related to concomitant therapy will be followed.

The sponsor must be notified in advance (or as soon as possible thereafter) of any instances in which prohibited therapies are administered.

9. STUDY EVALUATIONS

9.1. Study Procedures

9.1.1. Overview

The Time and Events Schedule summarizes the visits as well as the frequency and timing of assessments applicable to this study. A visit window of +/-12 calendar days will be allowed for all visits, unless otherwise indicated in the Time and Events Schedule. All visits are in principle single day visits however they may be performed over multiple days within the allowed visit window in cases of logistical issues or a subject's preference.

All subjects within the early (predementia) AD spectrum enrolled in this study being subjects asymptomatic at risk for AD and subjects with pAD, will follow the same procedures as listed in this section unless otherwise specifically indicated.

Information regarding handling, shipment, and labeling of biological samples (including safety labs) will be provided in a separate lab manual.

For CSF sampling, local site standard operating procedures (SOPs) may be applied for performing the actual lumbar puncture (not the collection), provided they are at least as restrictive as the criteria defined in this protocol or lab manual.

Separate imaging manuals and charters will be provided, describing the MRI imaging procedures, data acquisition and handling.

Any changes to the lab manual and imaging manuals/charters will not result in a protocol amendment.

In the event of abnormal safety findings during the conduct of the study, additional measurements may be made immediately and subsequently at a frequency considered appropriate by the attending physician.

The time points for individual measures may be changed (with or without affecting the overall frequency of these investigations) prior to and during the study based on newly obtained data (e.g., interim analysis, DRC) to allow for optimal fit to the actual safety or PK/PD profile of the study drug. This modification may result in a change in the overall frequency of the individual measures (e.g., safety measures, blood and CSF samplings) provided the maximal total blood and/or CSF volume collected per subject defined will not be exceeded. Such modifications, where performed only to allow optimal fit to the actual safety, PK/PD profile of the study drug, will not be considered to be an amendment to the protocol.

Cognitive testing should always be performed before medical procedures that could be stressful for the subjects (for example blood draws, CSF collection, etc.). If sedating medication is given for MRI at any visit or for any short-term use then all cognitive assessments must be administered/completed either before or at least 4 half-lives after administration of the sedative. Additionally, all neuropsychological testing and CSF collections should be performed at approximately the same time on each day these are performed. All neuropsychological tests should be administered by the same rater to reduce potential variability. In between different cognitive tests, adequate breaks should be taken to ensure optimal performance. Details on the different cognitive tests and functional outcome measures, alternative versions and forms to be used, sequence of performance, rater training and staff qualification required, will be described in a separate manual. Any changes to this manual will not result in a protocol amendment.

Venous blood will be collected for all blood-based analysis. When assessments occur at the same time point, the blood samples for PK and Biomarker analysis must always be collected as close to the scheduled time as possible, followed by the CSF sample for PK and Biomarker analysis. Other measurements may be done earlier than specified time points if needed. Actual dates and times of assessments will be recorded in the source documentation and CRF or lab requisition form.

Blood may be drawn by using a cannula or by venipuncture.

The exact times for each blood draw or assessment will be recorded in the CRF or lab requisition form. The order of multiple assessments within one protocol time point should also be the same throughout the study.

Vital signs will be recorded from the opposite arm from which the blood samples are being taken.

Blood pressures and ECGs should be recorded approximately 5 to 10 minutes before PK blood samples are taken.

Repeat or unscheduled samples may be taken for safety reasons or for technical issues with the samples.

The volume of blood collected per subject will be detailed in a separate lab manual.

For each subject, the maximum amount of blood drawn from each subject in this study will not exceed 450 mL per calendar year. For CSF no more than 24 mL annually (2 CSF collections) will be collected.

9.1.2. Screening Phase

Before any study specific procedures are conducted and following an explanation of the purpose and risks of the study, subjects will sign an informed consent form (ICF).

Subjects who provide consent to enroll in this protocol and who meet the inclusion criteria, may start at Day 1 of the DB treatment phase in lieu of the end of treatment visit in 54861911ALZ2002 study. For subjects who have completed the end of treatment visit in the 54861911ALZ2002 study, enrollment in this study should be completed (Day 1 of the DB treatment phase) as soon as possible, but within 6 weeks, following completion of their treatment period under the parent protocol of currently ongoing or any future Phase 1b or Phase 2 studies with JNJ-54861911. A screening phase of up to 12 weeks may be allowed following written approval of the Sponsor.

After giving initial written informed consent, subjects will be screened to assess their eligibility for the study according to the inclusion and exclusion criteria defined for this study.

Recording of adverse events/concomitant medication will start following consent and will continue until completion of the study.

During screening following assessments/procedures will be performed:

- Review of inclusion and exclusion criteria
- Complete/Review Medical History and Demographics
- Complete/Review Prestudy Therapy
- Review preplanned surgery/procedures
- Record adverse events and concomitant medication

Eligible subjects will be provided the opportunity to participate in the DB treatment phase and OL phase of the study described further below.

Subjects participating in this study may progress to a dementia state ($CDR \geq 1$) during course of the study. In such cases the informed consent may require a signature of the subject's legal representative as per local regulations.

9.1.3. Double-Blind Treatment Phase

Day 1

Subjects who successfully complete the screening examination will visit the clinical site on Day 1 of the DB treatment phase during the morning hours.

Prior to dosing following (baseline) assessments will be performed:

- C-SSRS (since last visit [or baseline if no C-SSRS was collected under the parent protocol])
- Blood sample collection for plasma JNJ-54861911 concentrations
- Blood sample collection for pharmacodynamics/biomarkers
- (Optional) CSF sample collection (~12 mL) by single lumbar puncture for PK/PD/biomarker assessment (baseline) after eligibility has been confirmed, provided no on-treatment sample was collected under the parent protocol
- 12-lead ECG recording
- Adverse event and concomitant medication will be reviewed

Following assessments will be performed prior to first dose in the current study at time points mentioned below only if no adequate assessments were conducted in ALZ2002 study (the assessments listed below 6 months and 9 months prior to dosing may also be performed during the screening period in case of any logistical issues):

1. At the last study visit of the treatment period:
 - Physical examination
 - Neurological examination
 - Body weight
 - Body temperature
 - Supine and standing vital signs (systolic and diastolic blood pressure and pulse)
 - Clinical safety laboratory assessments under fasted conditions, when feasible (including hematology, serum chemistry, and urinalysis)
2. 6 months prior to first dosing in this study (the assessments listed below may also be performed during the screening period in case of any logistical issues):
 - MRI
3. 9 months prior to first dosing in this study (the assessments listed below may also be performed during the screening period in case of any logistical issues):
 - Dermatological Examination

- Ophthalmological Examination (only in subjects completing the ALZ2002 parent study)
- Optical Coherence Tomography (OCT; at sites where OCT is available, in subjects completing the 54861911ALZ2002 parent study)

Eligible subjects will be assigned on Day 1 predose to the same treatment regimen in this study as received under 54861911ALZ2002 study as described in Section 6, Dosage and Administration.

Study medication will be dispensed (incl. drug accountability) and administered as outlined in Section 6, Dosage and Administration. Subjects will self-administer their study medication q.d. as instructed.

On Day 1 dosing will not be time limited and will be performed following completion of the baseline (predose) assessments.

Following dosing on Day 1 following assessments will be performed:

- 12-lead ECG recording at 2 to 4 hours postdose
- Blood sample collection for plasma JNJ-54861911 concentrations at 2 to 4 hours postdose
- MMSE*
- CFI*
- CDR*
- RBANS*

** This assessment scheduled on Day 1 may be performed either predose or postdose provided they have not been collected under the parent protocol 1) at the last study visit of the treatment phase or 2) 6 months prior to first dosing in this extension study.*

During DB treatment phase, following Day 1, subjects will return to the investigational site at regular time points as indicated in the Time and Events Schedule and further described below.

Week 8

Subjects will visit the site at Week 8 during the morning hours. Study medication will be self-administered on site as outlined in Section 6, Dosage and Administration.

Clinical safety laboratory assessments (hematology and serum chemistry) will be performed under fasted conditions, when feasible, as specified in the Time and Events Schedule. Assessments can be performed pre or post dose unless otherwise indicated.

Week 12

Subjects will visit the site at Week 12 during the morning hours. Study medication will be self-administered on site as outlined in Section 6, Dosage and Administration.

The following assessments will be performed at Week 12 as specified in the Time and Events Schedule. Assessments can be performed pre or post dose unless otherwise indicated.

- Drug accountability/Treatment compliance will be assessed. Study medication received on Day 1 will be handed in and new medication will be dispensed.
- C-SSRS (since Day 1)
- CVLT-II, in subjects who had this assessment in the parent study
- Adverse events and concomitant medication will be reviewed

Week 16

Subjects will visit the site at Week 16 during the morning hours. Study medication will be self-administered on site as outlined in Section 6, Dosage and Administration.

Clinical safety laboratory assessments (hematology and serum chemistry) will be performed under fasted conditions, when feasible, as specified in the Time and Events Schedule. Assessments can be performed pre or post dose unless otherwise indicated.

Week 24

Subjects will visit the site at Week 24 during the morning hours. Study medication will be self-administered on site as outlined in Section 6, Dosage and Administration.

The following assessments will be performed at Week 24 as specified in the Time and Events Schedule. Assessments can be performed pre or postdose unless otherwise indicated.

- Drug accountability/Treatment compliance will be assessed. Study medication received at Week 12 will be handed in and new medication will be dispensed.
- 12-lead ECG recording (2 to 4 hours postdose)
- Body temperature
- Supine and standing vital signs (systolic and diastolic blood pressure and pulse)
- Clinical safety laboratory assessments under fasted conditions, when feasible (including hematology, serum chemistry and urinalysis)
- Dermatological examination
- Ophthalmological examination(*) (only in subjects completing the ALZ2002 parent study)
- OCT (at sites where OCT is available, and only in subjects completing the ALZ2002 parent study)
- C-SSRS (since last visit)
- RBANS
- CFI
- Blood sample collection for plasma JNJ-54861911 concentrations (predose and 2 to 4 hours postdose)

- Blood sample collection for pharmacodynamics/biomarkers (predose)
- MRI
- Adverse events and concomitant medication will be reviewed

(An ophthalmological examination will only be performed if: 1) if there was an abnormality present at the screening/baseline examination; 2) if the investigator detects new ophthalmological findings or visual symptoms; 3) if OCT reveals new findings. The ophthalmologic examination should be performed by the same ophthalmologist who completed the initial ophthalmologic examination at screening/baseline.*

Week 36

Subjects will visit the site at Week 36 during the morning hours. Study medication will be self-administered on site as outlined in Section 6, Dosage and Administration.

The following assessments will be performed at Week 36 as specified in the Time and Events Schedule. Assessments can be performed pre or post dose unless otherwise indicated.

- Drug accountability/Treatment compliance will be assessed. Study medication received at Week 24 will be handed in and new medication will be dispensed.
- C-SSRS (since last visit)
- Clinical safety laboratory assessments under fasted conditions, when feasible (hematology and serum chemistry)
- Adverse events and concomitant medication will be reviewed

Week 52 (last visit [DB treatment phase])

Subjects will visit the site at Week 52 during the morning hours. Study medication will be self-administered on site as outlined in Section 6, Dosage and Administration. At Week 52 subjects will be dosed according to the treatment allocation assigned to in the DB treatment phase.

Randomization to OL treatment phase and dispensing of study medication for OL phase will only be performed following completion of all Week 52 assessments.

The following assessments will be performed at Week 52 as specified in the Time and Events Schedule. Assessments can be performed pre or postdose unless otherwise indicated.

- Physical and Neurological examination
- Body Weight
- 12-lead ECG recording (2 to 4 hours postdose)
- Body temperature
- Supine and standing vital signs (systolic and diastolic blood pressure and pulse)

- Clinical safety laboratory assessments under fasted conditions, when feasible (including hematology, serum chemistry and urinalysis)
- Dermatological examination
- (For subjects who completed the parent study, ALZ2002) Ophthalmological examination(*)
- (For subjects who completed the parent study, ALZ2002) OCT (at sites where OCT is available)
- C-SSRS (since last visit)
- RBANS
- MMSE
- CFI
- CDR
- Blood sample collection for plasma JNJ-54861911 concentrations (predose and 2 to 4 hours postdose)
- Blood sample collection for pharmacodynamics/biomarkers (predose)
- (Optional) CSF sample collection (~12 mL) by single lumbar puncture for PK/PD/biomarker assessment. Baseline and Week 52 [Month 12] CSF samples should be taken at approximately the same time of day (with an allowable window of 3 hours), with the Week 52 (Month 12) sample being collected postdose.
- MRI
- Adverse events and concomitant medication will be reviewed
- Drug accountability/Treatment compliance will be assessed. Study medication received at Week 36 will be handed in and new medication (for OL phase) will be dispensed.
- Randomization (OL phase): only following completion of all Week 52 assessments.

(*) *An ophthalmological examination will only be performed if: 1) if there was an abnormality present at the screening/baseline examination; 2) if the investigator detects new ophthalmological findings or visual symptoms; 3) if OCT reveals new findings. The ophthalmologic examination should be performed by the same ophthalmologist who completed the initial ophthalmologic examination at screening/baseline.*

Note: If a subject discontinues study treatment before completion of DB treatment phase or is withdrawn during DB treatment phase, he or she will be asked to complete the Month 12 (Week 52 assessments).

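### Day 1 baseline cognitive tests may be done after dosing, and so after the predose blood draws, against the protocol's own rule that cognition always comes first

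*Protocol*

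**What the plan says.** Section 9.1.1 (Overview) sets a general rule for all visits: "Cognitive testing should always be performed before medical procedures that could be stressful for the subjects". It names blood draws and CSF collection as examples of such procedures. The same paragraph asks for neuropsychological testing at roughly the same clock time on each testing day.

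Section 9.1.3, Day 1, lists the procedures to be done before dosing. They include a blood sample for drug concentration, a second one ("Blood sample collection for pharmacodynamics/biomarkers"), and an optional lumbar puncture for subjects with no on-treatment CSF sample from the parent study. On the order of events it says: "On Day 1 dosing will not be time limited and will be performed following completion of the baseline (predose) assessments".

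MMSE, CFI, CDR and RBANS then appear in the list of assessments that follow dosing. Their footnote reads "This assessment scheduled on Day 1 may be performed either predose or postdose", subject to the condition "provided they have not been collected under the parent protocol" at the last treatment-phase visit or in the 6 months before first dosing.

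In the Time and Events Schedule the four tests carry footnotes b or i on Day 1. Footnote b describes the assessment as a predose baseline. Footnote i repeats the 6-month condition and says nothing about dosing.

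**The concern.** For the affected subjects, these scores are the starting point for the exploratory objective on cognitive decline. The protocol itself treats blood draws and lumbar punctures as stressful enough to require that testing come before them, so no outside evidence is needed to see that the order matters to the sponsor. If some baselines are taken after these procedures and others before, or if baseline and follow-up are taken at different points in the visit, part of the measured change reflects test conditions and not the subject. This matters most for within-group change in the open-label phase, which has no placebo group to set it against.

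**Working it through.** The plan states no figure on this point, so the check is of the order of events.

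1. *What comes before the dose on Day 1.* By Section 9.1.3, the two blood samples are taken predose in all subjects. The schedule marks the Day 1 CSF sample with footnote c (predose required) and footnote k (only if the parent study gave no on-treatment sample). Any Day 1 puncture is therefore also predose.
2. *When the dose is given.* After the predose assessments are complete (Section 9.1.3).
3. *The postdose option.* The order is blood draws, puncture where done, dose, then the four tests. At least the blood draws come before testing in every such subject. This cannot be squared with the word 'always' in Section 9.1.1.
4. *The predose option.* Section 9.1.3 does not say where the tests fall within the predose list, but the general rule in Section 9.1.1 can be followed, so there is no contradiction here.
5. *The schedule.* Footnote b calls the baseline predose, which fits poorly with the Section 9.1.3 footnote. This conflict is softer: physical examination, vital signs and safety laboratory tests carry both b and c on Day 1, while the four tests carry b or i without c.
6. *Later visits.* Weeks 24 and 52 also allow assessments pre or postdose unless otherwise indicated, and also schedule predose blood draws. Week 24 has no puncture. At Week 52 the optional CSF sample is postdose, so predose testing would come before it.
7. *Clock time.* Later visits are morning visits. Day 1 is also a morning visit, but its dosing is not time limited, so a postdose test can drift later in the day.

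The effect on mean change can be written in symbols. Let p0 and pt be the shares tested after procedures at baseline and at follow-up, and d0 and dt the average loss of points that this causes. The measured mean change is then shifted by

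shift = p0 × d0 − pt × dt.

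The documents give none of the four quantities. The shift is positive if only the baseline is affected, near zero if both visits are affected alike, and negative if follow-up is affected more. For a comparison between arms, what counts is the difference in shift between arms. The same rule applies to every blinded arm, so nothing in the text makes that difference other than zero on average.

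**The case against.** The case on the other side is that few subjects are affected, the consequence is low, and site instructions may already settle the order.

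- *Few subjects.* Day 1 testing is needed only where the parent study gave no qualifying assessment. Enrolment is normally within 6 weeks of parent treatment, and the cognitive measures are aligned with the parent studies. A baseline taken after a puncture also requires a missing parent CSF sample, acceptance of an optional puncture, and postdose testing. This stands: the group is restricted, though the documents do not say how small it is.
- *A general rule and a manual exist.* Section 9.1.1 governs Day 1 too, and the sequence of tests is left to a separate manual that is not at hand. This answers the predose option. It does not answer the postdose option, where the Day 1 footnote gives a specific permission that breaks the general rule.
- *Low stakes.* Cognition is exploratory and summarised descriptively, with no formal hypothesis and no powering. The CDR does not rest directly on psychometric tests, and the CFI is reported by subject and study partner, so stress on the day may matter less for them. This also stands.

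A reader might infer that postdose testing depresses the baseline and so makes later change look too favourable to the drug. The documents do not support that. It requires follow-up scores to be taken before procedures while baseline scores are not, yet Weeks 24 and 52 carry the same latitude and the same predose blood draws. During the double-blind phase any effect would also fall on placebo and active arms under the same rule.

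**Conclusion.** The contradiction holds. For subjects without a qualifying parent-study assessment, Section 9.1.3 permits a baseline cognitive test that necessarily follows the predose blood draws, and the puncture in the subset who have one. Section 9.1.1 says this should never happen, and footnote b points the same way.

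The consequence is modest: avoidable noise in the baseline, and possible distortion of within-subject change, in exploratory endpoints. Its direction and size cannot be determined. One could assume that 10% to 40% of subjects are tested late at baseline only and lose 2 to 4 RBANS points, which gives 0.10 × 2 = 0.2 to 0.40 × 4 = 1.6 points. Every input there is a guess, so the range is not an estimate of bias in this trial. No bias between the blinded arms is shown.

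The conclusion rests on the order of events in the text alone. It assumes only that sites may use the permission as written.

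**What to change.** In Section 9.1.3, move RBANS, MMSE, CFI and CDR from the postdose list to the start of the Day 1 predose list. Reword their footnote along these lines: *done predose and before any blood draw or CSF collection, and only if not obtained under the parent protocol at the last treatment-phase visit or within 6 months before first dosing*. The condition must stay. Without it, Section 9.1.3 would call for Day 1 testing in everyone and conflict with schedule footnotes b and i.

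Align the schedule. Footnote b also serves other assessments, so a separate footnote for the four tests, carrying both the condition and the order, is cleaner than editing b and i.

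At Weeks 24 and 52, state that the freedom to assess pre or postdose does not override the cognition-first rule in Section 9.1.1, so that baseline and follow-up are taken at the same point in the visit.

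The change is one of wording and adds no procedure. The cost is tighter sequencing on Day 1 for the subjects who need these tests. Day 1 dosing is already not tied to the morning, which leaves room for it.
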